9.4.9 EXPLORATORY ANALYSES

Three classes of exploratory analyses will be executed in the modified intention-to-treat populations for the respective outcome measures:

- 1. Analyses of morbidity and mortality
- 2. Log-rank tests for non-covariate-adjusted differences in survival curves through 21 days postrandomization
- 3. Covariate-adjusted analyses

Morbidity and mortality will be analyzed following the procedure for the primary efficacy endpoint, in the modified intention-to-treat population for each endpoint.

Of primary interest for efficacy endpoints is the event rate at 21 days post-randomization. However, we will also report log-rank tests comparing survival curves between randomized arms throughout the follow-up period.

Cox proportional hazards fits will be reported, including effect estimates, standard errors, and tests for study arm, age, sex, race, and presence of at least one factor indicating membership in a high-risk group.

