1 PROTOCOL SUMMARY

1.1 SYNOPSIS			
Title:	RANDOMIZED DOUBLE-BLIND PLACEBO-CONTROLLED PROOF-OF-CONCEPT TRIAL OF RESVERATROL FOR THE OUTPATIENT TREATMENT OF MILD CORONAVIRUS DISEASE (COVID-19)		
Study Description:	•	trial to determine the safety and explore the efficacy of using itamin D3 to treat patients with mild COVID-19	
Objectives:	Primary Objective:	To compare the 21-day hospitalization rate among early or mild stage COVID-19 patients taking a 15-day regimen of resveratrol pus vitamin D3 to that for patients taking an identical placebo regimen.	
	Secondary Objectives:	Decrease morbidity and mortality in terms of reduced days of symptoms, reduced rate of ICU admission, reduced rate of mechanical ventilation, and reduced mortality.	
Endpoints:	Primary Endpoint:	Hospitalization rate	
	Secondary Endpoints:	ICU Admission rate, invasive ventilation rates, duration of symptoms, and mortality rates.	
Study Population:	200 hundred patients (100 per group) 45 years and older who test positive for SARS- COV2 who have mild COVID-19 based on WHO Baseline Severity Categorization		
Phase:	2		
Description of Sites/Facilities Enrolling Participants:	Outpatients presenting to COVID-19 testing sites of Mt Carmel Health Systems in Columbus, OH, which may include drive-thru testing centers, emergency departments, urgent care centers.		
Description of Study Intervention:	Patients will be placed on a 15-day course of two 500 mg resveratrol capsules 4 times per day, versus the same dosing frequency of placebo. Both groups will receive 100,000 IU on day one only.		
Study Duration	: up to 6 months		
Participant Duration:	60 days		

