3 OBJECTIVES AND ENDPOINTS			
OBJECTIVES	ENDPOINTS	JUSTIFICATION FOR ENDPOINTS	
Primary			
Reduction in hospitalization rates.	21-day hospitalization or death, defined as admission to any hospital for the treatment of COVID-19, or death, within 21 days of randomization for this study (date of randomization = day 0).	Based on reported typical course of illness for COVID-19 most patients will have declared their need for hospitalization in less than 21 days	
Secondary			
invasive ventilation rates, and ECMO usage rates admission to any intensive care unit (ICU) due to worsening symptoms of COVID-19, or death, among patients who are hospitalized within 21 days of randomization (date of randomization = day 0)		Based on reported typical course of illness for COVID-19 most patients will have declared their need for ICU admission/invasive ventilation/ECMO usage in less than 21 days	
Tertiary/Exploratory			
Reduction in morbidity and mortality	Reduction in signs and symptoms based on results of daily surveys. Will also observe mortality rates between groups.	There are mechanisms that would suggest improvements in morbidity and mortality, but this study will likely not have the statistical power to draw firm conclusions.	

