Participant Monitoring and Follow-up: Starting on day 1, and continuing daily for 15 days, subjects will be contacted via e-mail or text message (according to the subject's preference. Messages will include a reminder to take their study medication as scheduled and complete the daily survey (see appendix 12.6.1) each evening prior to going to bed. Subjects will be asked to complete a short questionnaire covering: 1) symptoms they had that day that may be related to COVID-19 (e.g., fever, cough, dyspnea), their frequency and severity; 2) report any other related or non-related medical events; 3) any medications they have taken to relieve symptoms, or other new medications they have not previously reported to study personnel; and 4) any visits they have made to healthcare providers, outpatient centers or hospitals, and details regarding those visits. Subjects will be reminded to contact their primary care physician if they experience symptoms that are worsening or that are concerning to them. For any such contact, they should inform their physician or other healthcare provider that they are enrolled in a clinical trial involving a dietary supplement.

Participants with complete on online PRO-CTCAE questionnaire on days 1, 8 (+1 day), 15 (+1 day), 21 (+1 day), 30, and 60 to monitor for adverse events.

Subjects who do not complete questionnaires will receive a reminder Xe-mails. All patients will be called for a phone interview after 21 days. If subjects cannot be contacted via phone, study personnel will attempt to contact the spouse/family member/friend who is listed as the secondary contact in order to determine the subject's status. A subject will be considered lost to follow-up if their status concerning hospitalization during the study period cannot be verified.

Outcome Assessment and Other Key Variables. Hospitalizations will be determined based on query of subject and/or the subject's secondary contact. The subject's medical records will be requested from the admitting hospital (and discharging hospital, if separate) via a HIPAA authorization.

Additional outcomes will include assessing number of days with fever and to assess symptoms, including dyspnea and fatigue. Questionnaires to assess symptoms will be based on the PRO-CTCAE (see appendix 12.6) (National Cancer Institute, 2020).

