8 STUDY ASSESSMENTS AND PROCEDURES

8.1 EFFICACY ASSESSMENTS

Outcome Assessment and Other Key Variables. Hospitalizations will be determined based on query of subject and/or the subject's secondary contact. The subject's medical records will be requested from the admitting hospital (and discharging hospital, if separate) via a HIPAA authorization.

Additional outcomes will include daily reporting of fever to assess number of days with fever and assess severity of dyspnea and fatigue. Questionnaires to assess symptoms and adverse events will be used to monitor patients based on the PRO-CTCAE (see appendix 12.6) (National Cancer Institute, 2020).

Conditions that the CDC defines as being high risk for developing severe COVID-19, and pertinent medications will be recorded.

Adverse events will be recorded using PRO-CTCAE and CTCAE.

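### Symptom duration is left to the primary endpoint's logistic procedure, which needs a yes/no outcome and has no rule for symptoms unresolved when the daily diary ends at day 15

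*Combined protocol and SAP*

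**What the plan says.** **Objective and tier.** The synopsis sets a secondary objective, "Decrease morbidity and mortality in terms of reduced days of symptoms", and gives the secondary endpoints as "ICU Admission rate, invasive ventilation rates, duration of symptoms, and mortality rates". Section 3 puts morbidity in the tertiary/exploratory tier, with the endpoint "Reduction in signs and symptoms based on results of daily surveys", and defines no duration variable. Symptoms appear neither in the secondary hypotheses (9.1) nor in the secondary analysis (9.4.3).

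**Data.** Section 8.1 states: "Additional outcomes will include daily reporting of fever to assess number of days with fever". It adds severity of dyspnea and fatigue. The daily survey prompts run as follows (4.1): "Starting on day 1, and continuing daily for 15 days". PRO-CTCAE questionnaires with a 7-day look-back are scheduled to day 60, for adverse events.

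**Analysis.** Section 9.4.9 says: "Morbidity and mortality will be analyzed following the procedure for the primary efficacy endpoint". It applies this in a modified intention-to-treat population. Section 9.4.2 specifies a logistic regression on age, sex, race, ethnicity, risk group and arm, multiple imputation from that model, and two kinds of sensitivity analysis: counting patients lost to follow-up as not hospitalized, and tipping-point analyses.

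**The concern.** Days of symptoms, or days with fever, are lengths of time, and a logistic model takes a yes/no outcome. To follow 9.4.9 the analyst must invent a cut-point, a definition of resolution, and a treatment of patients who are still ill at day 15, admitted or dead. Nothing in the plan stops those choices from being made after the data are seen.

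The gap may also act differently by arm. The plan's own assumption is 25% hospitalized on placebo and 10% on resveratrol, so any loss of diary data linked to admission would fall unequally. In a proof-of-concept trial capped at 200 patients, the symptom course could be one of the more informative efficacy results, so it deserves a method that fits it.

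**Working it through.** **1. The plan's own figure.** The documents give no number for symptom duration. The nearest is the power statement in 9.2: 80% for 25% versus 10%, with 95 complete per arm, two-sided 5%. The two-proportion formula gives

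Φ[(0.15·√95 − 1.96·√(2·0.175·0.825)) / √(0.25·0.75 + 0.10·0.90)] = Φ[(1.462 − 1.053)/0.527] = Φ(0.776) = 78.1%.

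Exactly 80% needs 9.7% on resveratrol, which rounds to the stated 10%. The figure reproduces, and its rates are used below. The point itself rests on reading the sections against each other.

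**2. Sections side by side.**
- Synopsis: morbidity is expressed as days of symptoms, a duration.
- 9.4.9: morbidity follows the primary procedure.
- 9.4.2: that procedure is logistic, for a binary outcome.
- 9.4.1: Kaplan-Meier is offered as a summary for censored data, with hospitalization as the example.
- 9.4.9: log-rank and Cox fits are listed as classes separate from morbidity and are not tied to symptom resolution.

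No section gives a symptom event, a cut-point or a rule for censoring at day 15.

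**3. Cost of dichotomizing (illustration).** Assumed: exponential time to resolution, placebo median 6, 8 or 12 days, 95 per arm. The probability of resolution by day 15 is a = 1 − 2^(−15/median) on placebo and b = 1 − 2^(−15·HR/median) on resveratrol. Binary power uses the formula in step 1. Time-to-resolution power is Φ[(√D/2)·ln HR − 1.96], with D = 95(a + b).

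Example, median 8 and HR 1.5: a = 0.73, b = 0.86, D ≈ 151. Binary power is 60%. Time-to-resolution power is Φ(2.49 − 1.96) = 70%.

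| HR for resolution | Resolved by day 15, yes/no | Time to resolution |
|---|---|---|
| 1.3 | 28–30% | 30–39% |
| 1.5 | 57–60% | 62–74% |
| 1.8 | 84–89% | 92–97% |

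Ranges run over the three medians. The binary column is unadjusted for covariates.

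**4. Possible bias from lost diary days.** Assumed: the diary stops at admission on day d, and symptoms persist to day 15. Uncounted days per patient = admission rate × (15 − d).

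| Admission day | Placebo, 25% | Resveratrol, 10% | Difference |
|---|---|---|---|
| 3 | 3.0 | 1.2 | 1.8 |
| 5 | 2.5 | 1.0 | 1.5 |
| 8 | 1.75 | 0.70 | 1.05 |

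More placebo days go uncounted, so a raw count works against resveratrol. With equal admission rates the difference is 0. With a 5-point difference and admission on day 5 it is 0.05 × 10 = 0.5 days.

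**5. Allowing recovery before day 15 (simulation, assumed values).** Both arms share a recovery median of 6, 8 or 12 days. Admitted patients (25% and 10%, admission uniform over days 3 to 8) are still ill at admission, and their remaining illness is drawn from the same distribution. The diary stops at admission or day 15. Mean recorded days are 6.7 to 8.9 on placebo and 7.0 to 9.6 on resveratrol, although true mean duration is about 0.8 days longer on placebo. Under these assumptions a raw count reverses the direction.

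**The case against.** **Diaries are not said to stop at admission.** A reader might infer that hospitalized patients stop reporting, so that bias is certain. The documents do not support this. Section 7.1 keeps patients in the study after treatment stops and asks for the remaining procedures, and the draft daily survey has an answer option for hospital admission. What remains is that no rule covers missing days. Section 7.2 also lets the investigator withdraw patients who become severe or critical, and then promises follow-up for outcomes and hospitalization only.

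**The primary procedure does handle missing data.** It has multiple imputation and tipping-point analyses, so it would be wrong to say that it ignores incomplete outcomes. But the imputation model does not include hospitalization, so missing symptom outcomes of admitted patients would be filled in as if they resembled others with the same covariates and arm. Imputation also does not turn a duration into a yes/no variable.

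**A binary analysis is feasible.** Section 9.4.9 says morbidity, not duration, and many diary items are yes/no. The claim that the analysis cannot be run at all is therefore too strong. It cannot be run on days, and no binary form is stated.

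**Time-to-event methods are in the plan.** Section 9.2 even calls the primary analysis Kaplan-Meier, in conflict with 9.4.2. This suggests that an unreconciled description lies behind the gap. It does not assign those methods to symptoms.

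**Symptom data continue after day 15.** The day-21 PRO-CTCAE look-back can show persistence, but it cannot give daily durations.

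**The stakes are limited.** Section 3 makes the endpoint exploratory and expects too little power for firm conclusions. This stands and lowers the severity.

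**Conclusion.** The mismatch is established from the text. A duration is named as an objective, its only assigned analysis is for a binary outcome, and no rule covers symptoms unresolved at day 15 or diary days missing after admission or death.

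The loss from dichotomizing is moderate: at an assumed hazard ratio of 1.5, about 57–60% power against 62–74%. The bias from lost diary days is conditional. It ranges from 0 to about 1.05–1.8 days per patient against resveratrol, and the upper figures need diaries to stop at admission, symptoms to last to day 15, and the full 25% versus 10% contrast. They describe a raw count of diary days, which the plan does not prescribe. The primary conclusion of the trial is unaffected. Severity is low to moderate.

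**What to change.** In 9.4.9, replace the morbidity sentence with the following:

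- **Endpoint.** Time from randomization to sustained resolution, dated at the first of 3 consecutive diary days without the listed symptoms. Sections 4.4 and 6.4 already use a 3-day run. The listed symptoms are those the patient reports at baseline, plus any fever, dyspnea or fatigue that emerges later, with a severity threshold fixed in advance. The baseline part matters because mild COVID-19 at entry excludes dyspnea and may involve only cough or sore throat. Without it, patients with no fever or fatigue at entry would resolve at once.
- **Analysis.** Kaplan-Meier and log-rank, with a covariate-adjusted Cox model, in the ITT population. Section 9.3 defines ITT but not the modified ITT population that 9.4.9 uses.
- **Incomplete follow-up.** Censor at day 15, with the day-21 PRO-CTCAE as supportive evidence of persistence. Treat deaths and hospitalized patients as unresolved through day 15. Add a sensitivity analysis that uses hospitalized patients' diary entries where completed.
- **Mortality.** Keep the logistic procedure.
- **Tier.** Reconcile the synopsis (secondary) with section 3 (exploratory).

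The cost is SAP wording, since the data are already to be collected. The downside is that resolution during a hospital stay is not credited in the main analysis, and the endpoint partly overlaps with hospitalization. This is a cheap improvement.

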1.2 SCHEMA

Prior to Enrollment Screening

•Total n=200

• Review electronic report of newly positive SARS-CoV2 test results of patients 45 and older

- •If old records are available, clinicians to prescreen for exclusion criteria
- •Contact potenially eligible participants by phone to discuss interest in study
- •Patient referred to an online site to review a video discribing the study, risk, benefits.
- Patient given the opportunity to ask questions
- •Obtain informed consent electronically
- •Screen potential participants by inclusion and exclusion criteria
- •Obtain history, document

Randomization

•Intervention Group 1 (n=100)

•Placebo (n=100)

Day1

Baseline Survey & Start treatment

•Patient take Vitamin D3 100,000 IU on day and starts treatment or placebo

• Patients will receive an baseline assessment using Patient-Reported Outcomes version of the Common Terminology Criteria for Adverse Events (PRO-CTCAE[™]).

Day 2-15

Treatment or placebo and daily online survey

•Participant to take 2 capsules of intervention or placebo 4 times per day for 15 days.

• Participant will receive a daily online survey to assess for signs and symptoms of COVID-19 and to report potential side effects. If a patient has not completed an online survey within 24 hours, the patient will be contacted via phone to check their status.

Day 8, 15, 21

Weekly PRO-CTCAE Survey

•Patients will questionnaire with 7 day look back of adverse events based on the Patient-Reported Outcomes version of the Common Terminology Criteria for Adverse Events (PRO-CTCAE[™]).

Between day 21-30 Follow-up assessments for efficacy

•Clinicians will perform a chart review to assess patient outcomes as well as contact patient for an exit interview via phone.

Day 30 and Day 60

Long term assesment

[figure not shown]
• Participant Completes PRO-CTCAE to evaluate for adverse events

Study Completion Follow-up assessments of study endpoints and safety

•Data analysis

• Possible long term follow up of adverse events as outlined in section 8.3

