9.4.2 ANALYSIS OF THE PRIMARY EFFICACY ENDPOINT(S)

The primary efficacy endpoint is hospitalization for any cause within 21 days after randomization, as established by medical record review. Outcomes of subjects who withdraw consent or are otherwise lost to follow-up before 21 days will be considered missing. The intention to treat population for the hospitalization endpoint will be used for analysis. A logistic regression model will be fit with age, sex, race, ethnicity, risk group (see Sec 9.4.7), and randomized group as covariates, with the coefficient to randomized group as the primary estimand. Missing outcome data will be imputed using multiple imputation based on predictions from the logistic regression model of the outcome. Sensitivity analyses will include analyses in which patients lost to follow-up are assumed to not have been hospitalized, and tipping-point analyses systematically and comprehensively varying assumptions about missing outcomes on the treatment and placebo arms independently.

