Runny nose (rhinorrhea)	0	0	0
Sore throat	0	0	0
Cough (new onset or worsening of chronic cough)	0	0	0
Shortness of breath (dyspnea)	0	0	0
Nausea or Vomiting	0	0	0
Headache	0	0	0
Abdominal pain	0	0	0
Diarrhea (>3 loose/looser than normal stools/24hr period)	0	0	0

What's your highest temperature within the past 24 hours? (If you have access to a thermometer)

(Farenheight temperature)

06-19-2020 10:50

Page 2 of 3

Overall how do you feel compared to yesterday?	Much worse	Same	Much better	
			lace a mark on the scale above)	
TODAY, what was the SEVERITY of your SHORTNESS OF BREATH, at its WORST	 None Mild Moderate Severe, Very Severe 			
TODAY, how much did your SHORTNESS OF BREATH INTERFERE with your usual or daily activities	 Not at all A little bit Somewhat Quite a bit Very much 			
TODAY, what was the SEVERITY of your FATIGUE, TIREDNESS, OR LACK OF ENERGY at its WORST?	 None Mild Moderate Severe, Very Severe 			
TODAY, how much did FATIGUE, TIREDNESS, OR LACK OF ENERGY INTERFERE with your usual or daily activities?	 Not at all A little bit Somewhat Quite a bit Very much 			
TODAY, how OFTEN did you have LOOSE OR WATERY STOOLS (DIARRHEA/DIARRHOEA)?	 Never Rarely Occasionally Frequently Almost constantl 	У		
Other symptoms - 1	0		M	
Other symptoms - 1, specify:			2	
Other symptoms - 2	0			
Other symptoms - 2, specify:				
Other symptoms - 3	0	کہ		
Other symptoms - 3, specify:				
Have you had to seek medical attention in the past 24 nours?	Yes, called a help Yes, when to an Yes, I was admitt None of the aboy	urgent care / er ed to the hospi	nergency departmer tal	
Other:				
	.	3		

06-19-2020 10:50

projectredcap.org

NIH-FDA Clinical Trial Protocol Template – v1.0 2017-04-07

Page 3 of 3

Have you have any other medical events within the past 24 hours (not previously reported)? This could include items not necessarily related to COVID-19, such as a car accident, broken bone, or new/worsening of another medical condition.

National Center for Immunization and Respiratory Diseases (NCIRD), Division of Viral Diseases

06-19-2020 10:50

projectredcap.org **REDCap** 84 | Page

6.2 – PRO-CTCA		(1, 8, & 15, 21, 30, AND 60)	
fidential	These are DRAFT exampl will be finalized before p	atient enrollment Resveratroi for COVID-	
PRO-CTCAE	CTCAE Note that questions will be formatted for		
	electronic viewing and w	ill have conditional	
Study ID	formatting such that only relevant questions will		

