In the last 7 days, how OFTEN did you have PAIN?	 Never Rarely Occasionally Frequently Almost constantly 	
In the last 7 days, what was the SEVERITY of your PAIN at its WORST?	 None Mild Moderate Severe, Very Severe 	

	Page 5 of	
In the last 7 days, how much did PAIN INTEREFERE with your usual or daily activities?	 Not at all A little bit Somewhat Quite a bit Very much 	
In the last 7 days, how OFTEN did you have a HEADACHE?	 Never Rarely Occasionally Frequently Almost constantly 	
In the last 7 days, what was the SEVERITY of your HEADACHE at its WORST?	 None Mild Moderate Severe, Very Severe 	
In the last 7 days, how much did your HEADACHE INTERFERE with your usual or daily activities?	 Not at all A little bit Somewhat Quite a bit Very much 	
In the last 7 days, how OFTEN did you have ACHING MUSCLES?	 Never Rarely Occasionally Frequently Almost constantly 	
In the last 7 days, what was the SEVERITY of your ACHING MUSCLES at their WORST?	 None Mild Moderate Severe, Very Severe 	
In the last 7 days, how much did ACHING MUSCLES INTEREFERE with your usual or daily activities?	 Not at all A little bit Somewhat Quite a bit Very much 	
In the last 7 days, how OFTEN did you have ACHING JOINTS (SUCH AS ELBOWS, KNEES, SHOULDERS)?	 Never Rarely Occasionally Frequently Almost constantly 	
In the last 7 days, what was the SEVERITY of your ACHING JOINTS (SUCH AS ELBOWS, KNEES, SHOULDERS) at their WORST?	 None Mild Moderate Severe, Very Severe 	
In the last 7 days, how much did ACHING JOINTS (SUCH AS ELBOWS, KNEES, SHOULDERS) INTEREFERE with your usual or daily activities?	 Not at all A little bit Somewhat Quite a bit Very much 	

Confidential

Page 6 of 7

20	
In the last 7 days, what was the SEVERITY of your FATIGUE, TIREDNESS, OR LACK OF ENERGY at its WORST?	 None Mild Moderate Severe, Very Severe
In the last 7 days, how much did FATIGUE, TIREDNESS, OR LACK OF ENERGY INTERFERE with your usual or daily activities?	 Not at all A little bit Somewhat Quite a bit Very much
In the last 7 days, did you BRUISE EASILY (BLACK AND BLUE MARKS)?	○ Yes ○ No
In the last 7 days, how OFTEN did you have NOSEBLEEDS?	 Never Rarely Occasionally Frequently Almost constantly
In the last 7 days, what was the SEVERITY of your NOSEBLEEDS at their WORST?	 None Mild Moderate Severe, Very Severe
In the last 7 days, how OFTEN did you have SHIVERING OR SHAKING CHILLS?	 Never Rarely Occasionally Frequently Almost constantly

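### The exploratory symptom analysis makes no use of the day-1 PRO-CTCAE scores the trial already collects, and so gives up some power

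*Combined protocol and SAP*

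**What the plan says.** Section 3 lists a tertiary/exploratory endpoint: "Reduction in signs and symptoms based on results of daily surveys". Section 8.1 adds days with fever and says the trial will "assess severity of dyspnea and fatigue".

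On analysis, section 9.4.9 states: "Morbidity and mortality will be analyzed following the procedure for the primary efficacy endpoint". The procedure it points to is in section 9.4.2: "A logistic regression model will be fit with age, sex, race, ethnicity, risk group (see Sec 9.4.7), and randomized group as covariates". The separate Cox fits in 9.4.9 report "tests for study arm, age, sex, race, and presence of at least one factor indicating membership in a high-risk group". Neither list contains a baseline symptom term.

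On data, the schema in section 1.2 says of day 1: "Patients will receive an baseline assessment using Patient-Reported Outcomes version of the Common Terminology Criteria for Adverse Events". Section 4.1 schedules the same form on days 1, 8, 15, 21, 30 and 60. Its fatigue item (appendix 12.6) reads "In the last 7 days, what was the SEVERITY of your FATIGUE, TIREDNESS, OR LACK OF ENERGY at its WORST". The daily survey asks "TODAY, what was the SEVERITY of your FATIGUE, TIREDNESS, OR LACK OF ENERGY at its WORST". Both have the same five response levels. The PRO-CTCAE form also grades cough, muscle aches, headache and chills. It has no fever item.

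**The concern.** The covariate list in 9.4.2 was written for hospitalization, which has no baseline value because everyone enters as an outpatient. Symptoms do have one. Section 5.1 admits participants up to 7 days after onset, and mild disease there covers a range of symptoms, so the starting load should differ between people. Age, sex, race, ethnicity and risk group do not measure it. Section 4.1 says that allocation is stratified but names no factors, so nothing in the documents shows that randomization balances it either.

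Section 3 itself concedes that firm conclusions on morbidity are unlikely at this sample size. A prognostic measure that is already in the database, and costs participants nothing, is then worth using. Naming it in advance also closes off a post hoc choice of covariates.

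**Working it through.** **Inputs from the documents.** 100 randomized per arm, 5% loss, 95 evaluable per arm, 25% against 10% hospitalized, 80% power (sections 1.1 and 9.2); two-sided 5% tests (9.4.1). No power figure, effect size or correlation is given for symptoms.

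**The plan's own figure, as a check.** Two-proportion Z test, pooled variance under the null, 95 per arm:

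- z = [0.15 × √95 − 1.96 × √(2 × 0.175 × 0.825)] / √(0.25 × 0.75 + 0.10 × 0.90) = (1.462 − 1.053) / 0.527 = 0.776, so power is 78.1%.
- Exactly 80% needs a resveratrol rate of 9.7%. The stated 80% is therefore reproduced to within 2 points. It concerns hospitalization and is not affected by this point.

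**Assumption.** Rho is the correlation between the baseline item and the follow-up symptom level that remains after the planned covariates. It is varied from 0.2 to 0.7.

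**Continuous symptom score.** The effect giving 80% power without baseline is d = (1.960 + 0.8416) × √(2/95) = 0.4065 SD. Adjustment multiplies the variance by (1 − rho²), so power = Φ(2.8016 / √(1 − rho²) − 1.96).

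| rho | Variance factor | Power at 0.41 SD | Detectable at 80% power |
|---|---|---|---|
| 0 | 1.00 | 80% | 0.41 SD |
| 0.2 | 0.96 | 82% | 0.40 SD |
| 0.3 | 0.91 | 84% | 0.39 SD |
| 0.5 | 0.75 | 90% | 0.35 SD |
| 0.7 | 0.51 | 98% | 0.29 SD |

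For a smaller effect of 0.30 SD, power goes from 54% to about 67% at rho 0.5.

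**Dichotomised outcome by logistic regression**, the form that 9.4.2 implies. This was simulated with 95 per arm, an assumed 50% control rate, a latent shift of 0.41 SD and 3,000 trials per rho. Models had arm alone, or arm plus baseline. Power is given as the range over two runs; the other columns come from one run.

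| rho | Power without baseline | Power with | SE of log odds ratio | SD of standardised risk difference |
|---|---|---|---|---|
| 0.3 | about 60% | 62–63% | 0.300 to 0.312 | 0.0708 to 0.0693 |
| 0.5 | about 60% | 67–68% | 0.300 to 0.333 | 0.0695 to 0.0641 |
| 0.7 | about 60% | 77–78% | 0.300 to 0.379 | 0.0712 to 0.0591 |

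At rho 0.5 the variance of the risk difference falls by 1 − (0.0641/0.0695)² = 15%, against 25% for a continuous score. The standard error of the log odds ratio rises on adjustment; power still improves because the conditional estimate moves further from zero.

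**Chance imbalance.** The difference in baseline means has SD √(2/95) = 0.145, so a gap above 0.2 SD in either direction occurs with probability 2 × [1 − Φ(0.2/0.145)], about 17%. Over randomizations this is noise, not bias.

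**The case against.** The case against is mostly about size and scope, and much of it stands.

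- **The planned model is logistic.** A reader might infer from the continuous-score figures that the planned treatment coefficient loses precision. It does not: the standard error of the log odds ratio is smaller without the baseline term. The loss is in power and in the standardised risk difference, and is somewhat smaller than the continuous figures suggest at low to middle rho.
- **Rho is not in the documents, and could be low.** The baseline item asks for the worst of the last 7 days and the daily item asks about today. Section 6.4 expects many participants to have a short illness, which would push later scores towards zero. At rho 0.2 the gain is about 2 points for a continuous score.
- **The symptom outcome is undefined.** Section 3 gives no time point, summary or outcome type. That has to be settled before any covariate can be specified. In the daily survey, cough and muscle aches are yes/no items while fatigue is graded, so the form of the model will differ by symptom.
- **A usable baseline does not exist for every named symptom.** A reader might want chills as a stand-in for fever days, or cough or fatigue for dyspnea. The documents give no support for either. Dyspnea at entry is nearly constant, because section 5.1 defines mild disease as without shortness of breath.
- **The day-1 form is not stated to precede dosing.** The schema puts the baseline survey and the start of treatment on the same day, and appendix 12.6 marks the forms as draft.

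None of this answers the omission itself. No section adds a baseline symptom covariate, and the covariate-adjusted class in 9.4.9 does not either.

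**Conclusion.** The point holds as a near-free improvement to an exploratory analysis. The trial collects day-1 symptom severity and plans no use of it in comparing symptoms between arms. For fatigue, where the baseline and daily items match apart from the recall period, the gain is about 4 points of power at rho 0.3 and 10 at rho 0.5 for a continuous score. For a dichotomised outcome it is about 3 and 8 points. Both rest on an assumed rho beyond the planned covariates, and the second also on an assumed 50% control rate.

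Two stronger readings are not supported. The first is that the omission biases the symptom comparison or threatens the trial's conclusion. Randomization protects the test, section 9.4.1 makes no multiplicity-controlled claim for exploratory analyses, and hospitalization is unaffected. The synopsis does list duration of symptoms as a secondary endpoint, but sections 3 and 9.4.9 treat symptoms as exploratory. The second is that adjustment would cure the limited power conceded in section 3: at 0.30 SD and rho 0.5, power is still only about 67%.

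**What to change.** In section 9.4.9:

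1. Define each symptom outcome (graded score, yes/no or number of days, and over which days), since the covariate depends on it.
2. For each symptom model with a usable matching day-1 PRO-CTCAE item, add that item as a prespecified covariate alongside those of 9.4.2: fatigue first, then items such as cough and muscle aches. Do not require proxy baselines for fever days or dyspnea.
3. State that the day-1 PRO-CTCAE form is completed before the first dose. Do not use the day-1 daily survey as baseline, because section 4.1 has it filled in that evening, when treatment may already have started.
4. Give a simple rule for a missing baseline, for example mean fill-in or a missing indicator.
5. For a binary outcome, report the standardised risk difference with the odds ratio.

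Leave the hospitalization model as it is. The cost is plan wording, one covariate per symptom model and an instruction on form timing. No new data or participant burden is needed. Step 1 is the larger piece of drafting, but the symptom analysis needs it in any case.
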